Data and Safety Monitoring Board (DSMB): The Data and Safety Monitoring Board (DSMB) will act in an advisory capacity to the National Institute of Diabetes, Digestive and Kidney Diseases (NIDDK) to monitor subject safety and evaluate the efficacy of the intervention being studied in this clinical trial funded by the NIDDK. The DSMB will be appointed by the PIs upon study funding, and approved by NIDDK program staff. The DSMB will be composed of at least two experienced clinical nutrition support investigators not otherwise participating in the study and not affiliated with Emory. A biostatistician not otherwise participating in the study will also be named to the DSMB. The DSMB will meet twice yearly, and as needed, and will receive blinded and unblinded reports on study progress prepared by the DCC.

Statistical Analysis:

Continuous variables will be summarized with standard descriptive statistics and represented graphically with displays such as scatterplots, box plots, line plots and histograms, while categorical variables (adverse events) will be described by frequency tables.

For Aim 1: The primary analyses of the data will be performed according to subjects' original treatment assignment (i.e., intention-to-treat analyses) and the inclusion of all data from all subjects randomized in the final analysis. Rates of infection (i.e., BSI and total nosocomial infections) per 1000 hospital days will be estimated overall and for each of the 3 energy doses. Confidence intervals (95%) for the incidence rates will be estimated using an exact method based on the Poisson distribution.

Additionally incidence rates of infection will be estimated by performing a generalized estimating equations (GEE) Poisson regression analysis of the counts, implemented using SAS Proc Genmod, using an exchangeable correlation structure for the repeated counts within subject. The incidence rate ratio (IRR) is the ratio of the incidence density in one group to that of another group. Results by each baseline covariate will be presented as the IRR and the 95% confidence interval (CI). This GEE model can also accommodate time-dependent covariates such as daily blood glucose levels measured before an infection and total 28-day energy (cumulative deficit or as a time-dependent covariate).

Twenty-eight day mortality will be summarized as a proportion plus the 95% confidence interval (overall and for each treatment group). The 28-day mortality will be compared between treatment groups using a chi-square or Fisher's exact test. The potential association of each of the categorical prognostic factors (gender, race, high or low Apache score, clinical center) with mortality will also be evaluated using a Chi-square test or Fisher's exact test. Baseline continuous prognostic factors (age, SOFA score, blood glucose) will be compared by treatment group using the Wilcoxon rank-sum test. Odds ratios will be calculated to measure the degree of association. All statistical tests will be 2-sided. Factors significant to at least a value of $P \leq 0.20$ in the univariable analyses will be used in multivariable logistic regression analyses. Forward and backward stepwise selection will be used if necessary to choose prognostic variables for a multivariable logistic regression model. The odds ratio and its 95% confidence interval will be calculated for each factor in the presence of others in the final model.

Days on mechanical ventilation, length of ICU stay and hospital length of stay will be summarized with percentiles (25th, 50th and 75th) and the median absolute deviation. These secondary outcomes will be compared between the 3 treatment groups using the Kruskal-Wallis test. Repeated-measures analyses of daily SOFA scores and laboratory measures such as blood glucose will be analyzed with a means model with SAS Proc Mixed (version 9, mixed linear models) providing separate estimates of the means by time on study (days 0, 3, 7, 14, 21, and 28) and treatment group (energy dose: 0.6, 1.0 and 1.3 x REE). An unstructured variance-covariance form among the repeated measurements will be assumed for each outcome and estimates of the standard errors of parameters will be used to perform statistical tests and construct 95% confidence intervals. T-tests will be used to compare the pairwise differences between the model-based treatment means (least-squares means) at each time point. Statistical tests will be 2-sided. The model-based means are unbiased with unbalanced and missing data, so long as the missing data are non-informative (missing at random). A dropout process is assumed to be missing at random if; conditional on the observed data, the dropout is independent of the unobserved measurements.

For Aim 2: The agreement between the study entry HBE and the initial REE, as well as the mean daily serial MREE by metabolic cart, will be summarized using graphical methods and by calculating the 95% limits of agreement estimated by the mean difference ± 1.96 standard deviation of the differences. Bland and Altman (1999)⁶³ extend the limits of agreement approach to data with repeated measurements (i.e., serial REE measurements). To investigate whether the relationship between mean daily serial REE and entry HBE is altered by the mean daily caloric dose administered, regression methods will be used (i.e., analysis of covariance, ANCOVA). ANCOVA analyses will also be stratified by location (ICU versus the floor).

For Aim 3: The data processing will be performed as follows: 1) Feature detection conducted by systematic re-extraction with multiple parameter settings that optimize sensitivity and reliability; 2) Sample quality and feature consistency evaluation; 3) Feature overlap detection between datasets; 4) Statistical analysis includes false discovery rate (FDR; typically with $q=0.05$) to identify significantly different features between the two groups while correcting for multiple comparisons; hierarchical cluster analysis (HCA) to visualize differences between groups as

well as between time points and to identify clusters of highly correlated features that can be mapped to biological pathways; 5) Characterization of features and biological pathways utilizing multiple chemical databases (KEGG) metabolic pathways

(http://www.genome.jp/kegg/tool/color_pathway.html), MetaCore (www.genego.com; Carlsbad, CA), and MetaCyc (<http://www.metacyc.org>).⁶⁹ We will utilize Metaboanalyst 2.0⁷⁰ for the time series analysis to detect metabolic changes throughout the study period and two-way ANOVA to determine the impact of varying energy doses on global metabolomics patterns. Once important features have been identified, we have the ability to positively identify the chemical names of known metabolites by MS/MS analysis.

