Comparative effectiveness of energy doses in critical illness

Short title: The Energy Dose Study

Principal Investigator: [name].

Protocol Version Date: 6/2/2014

NCT Number: NCT01369147

Abstract:

Protein and/or energy deficits are associated with increased rates of hospital infection, skeletal muscle weakness, impaired wound healing, and prolonged convalescence in ICU patients. To prevent or treat malnutrition, enteral nutrition (EN) and/or parenteral nutrition (PN) are routinely given worldwide to a significant proportion of ICU patients. Optimal caloric requirements in critically ill patients are unknown due to a lack of rigorous randomized clinical trials. The comparative efficacy of energy doses in critically ill patients is unknown and clinical recommendations are conflicting and controversial; this issue is the focus of our study.

We have designed this pilot, single-center Randomized Clinical Trial (RCT) to prospectively compare, for the first time, the clinical efficacy of different energy doses in ICU patients requiring PN due to intestinal failure/dysfunction. A total of 60 patients will be studied (20 per energy dose group) to generate critical preliminary data needed to inform subsequent appropriately powered Phase III multicenter trials.

The primary aim of this study is to perform a controlled, double-blind, prospective, randomized, intent-to-treat Phase II clinical trial to test the efficacy of three specific energy doses [0.6, 1.0 and 1.3 x measured REE (resting energy expenditure), respectively], given for 28 consecutive days during the ICU course, on 28-day total hospital-acquired infections (primary endpoint), Blood Stream Infections (BSI), and other important clinical outcomes in medical/surgical ICU patients requiring specialized parenteral \pm enteral feeding. We would also determine, in these subjects A) the impact of cumulative and mean daily 28-day energy deficits [energy intake-measured REE] on clinical outcome endpoints; and B) the practical utility of estimated REE determined by Harris-Benedict equation versus measured REE across different energy doses. We would also like to determine the impact of administered energy dose and energy deficits on global metabolomic patterns over time and their association with key clinical outcomes.

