Unfortunately, in all trials concerning ICU energy dose and outcomes, **a major design flaw is that the amino acid/protein and micronutrient intake has also varied between groups, especially when enteral feeds were employed**³⁴. Also, blood glucose levels in the study groups, a known risk factor for ICU morbidity and mortality, were either not reported^{6, 11, 35} or were higher than levels now considered appropriate for ICU patients (<150-180 mg/dL)³⁶. **Thus, the true impact of energy dose per se on clinical outcomes in ICU patients is unknown at the present time.** Studies to help better define energy dosing are also potentially important to guide clinicians to avoid complications related to overfeeding and refeeding syndromes, common in ICU settings^{12, 37-39}. **Phase III, adequately powered, double-blind, intent-to-treat RCTs are needed, with design informed by pilot data such as we will generate in this project, to better define calorie requirements associated with improved outcomes in ICU patients.**

Recent discussions have emphasized the utility of metabolomic methods for nutrition research^{40, 41}. **Metabolomics analysis represents a novel approach to study integration of metabolic responses to specialized nutrition support**^{42, 43}. We, under the direction of Co-I [name], have focused on high-resolution liquid chromatography mass spectroscopy (LC-MS) method. Metabolic profiles can be analyzed using our established bioinformatics methods to identify metabolic patterns and potential metabolic biomarkers of energy insufficiency and response to the different ICU energy dose regimens⁴⁴. **The proposed studies will allow us to generate needed data on the effect of energy dose and energy deficits on global metabolomic patterns over time that may be associated with key clinical outcomes in ICU patients.** Future studies could focus on nutritional strategies based on the specific identity of plasma metabolites that may be associated with improved outcomes. The fractal analysis-derived Hurst exponent has recently received attention because it provides a means to interpret biological signals generated by healthy biological systems or pathological states with one numerical value⁴⁵⁻⁴⁹. Hurst exponent data is related to a variety of physiologic states and to outcome measures in Parkinson's disease, obstructive sleep apnea and sudden

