cardiac death⁴⁵⁻⁴⁹. Fractal analysis of metabolomic data will allow us to test whether the Hurst exponent is related to clinical outcomes and/or response to nutritional interventions in the ICU patients we propose to study.

Emerging data strongly suggest that microbes of the intestine (the microbiota) play a key role in host metabolism, immune/inflammatory processes and disease pathophysiology⁵⁰⁻⁵². The intestinal microbiome (genome of the gut microbiota) is shaped by both environment (e.g. diet) and host genetics; and, vice versa, the gut microbiota itself appears to regulate a wide spectrum of host immune, inflammatory and metabolic responses⁵³. **Human data on the impact of nutrition support during critical illness on the gut microbiome are limited.**

Despite limited evidence, there is a suspected interplay between critical illness and the gut microbiome, which warrants further exploration in the setting of nutrition support⁵⁴⁻⁵⁸. Nelson et al utilized 16S rRNA pyrosequencing to characterize stool of hospitalized patients and observed perturbations in gut microbiota following infection⁵⁹. It is acknowledged that the microbiome plays an integral role in health maintenance, and that modifications of the gut microorganisms may influence outcomes in critically ill patients.

Hypothesis:

- 1) Adequate energy administration (defined as 1.3 x REE) will result in a lower 28-day total hospital-acquired infection rate compared with ICU patients receiving lower energy doses.
- 2) Differences in energy intake will result in global changes in metabolic patterns that themselves are associated with clinical outcomes in the ICU patients studied.

Specific Aims:

- 1) To perform a controlled, double-blind, prospective, randomized, parallel group, intent-to-treat Phase II clinical trial to test the efficacy of three specific energy doses [0.6, 1.0 and 1.3 x measured REE (metabolic cart), respectively], given for 28 consecutive days during the ICU course, on 28-day total hospital-acquired infections (primary endpoint), BSI, and other important clinical outcomes in medical/surgical ICU patients requiring specialized parenteral ± enteral feeding.
- 2) In Aim 1 subjects to: a) examine the impact of cumulative and mean daily 28-day energy deficits [energy intake-measured REE] on clinical outcome endpoints; and b) to estimate the agreement for REE as determined by the HBE and the measured REE across different energy doses.

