- 3) To determine the impact of administered energy dose and energy deficits on global metabolomic patterns, human microbiome, and handgrip strength over time and their association with key clinical outcomes in Aim 1 subjects.

Study Procedures:

A total of 60 subjects will be enrolled in this intent-to-treat trial at Emory University Hospital (EUA) and EUA-Midtown. Patients admitted to either a medical or surgical (non-neurological)

ICU within the previous 168 hours and who are expected to survive and remain in the ICU for at least 96 hours after entry are eligible. Patients enrolled in this study are also those deemed to likely require central venous parenteral nutrition (PN) for 7+ subsequent days after entry on a clinical basis. Patients who meet the following eligibility criteria will be approached:

[figure not shown]
Inclusion criteria: 1) A signed informed consent is in place on the patient's chart; 2) The patient is at least 18 but not more than 90 years of age at time of ICU admission; 3) The patient has a body mass index (BMI) > 40 kg/m²; 4) The patient has been admitted to either a medical or surgical (non-neurological) ICU and is expected to survive and remain in the ICU for at least 72 hours after entry; 5) There is central venous access for administration of the study PN; 6) The patient's primary physician(s) will allow the investigative team to manage the study PN and enteral feedings during the current hospitalization; and 7) The patient is expected to require total or partial central venous PN for 7 or more subsequent days after entry on a clinical basis (e.g. following massive small bowel ± colonic resection, the presence of high output fistulae or perforated small bowel, with demonstrated intolerance to EN or when EN may be contraindicated, as with severe diarrhea or emesis, partial or complete bowel obstruction, severe gastrointestinal bleeding and severe hemodynamic instability, such as with escalating vasopressor requirements).

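### Inclusion criterion 3 admits only patients with BMI above 40 kg/m², while the rest of the protocol describes medical and surgical ICU patients in general

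*Combined protocol and SAP*

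**What the plan says.** The numbered inclusion criteria under Study Procedures are introduced with "Patients who meet the following eligibility criteria will be approached", so they are entry conditions. The third is "The patient has a body mass index (BMI) > 40" kg/m². The exclusion criteria contain no BMI limit, and no later section corrects or explains the third criterion.

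Elsewhere the population is broader:
- The Abstract says the trial compares "the clinical efficacy of different energy doses in ICU patients requiring PN due to intestinal failure/dysfunction".
- Specific Aim 1 refers to "other important clinical outcomes in medical/surgical ICU patients requiring specialized parenteral ± enteral feeding".
- The Background says that Phase III trials, informed by these pilot data, are needed "to better define calorie requirements associated with improved outcomes in ICU patients".

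The same section also states the expected ICU stay twice. The opening paragraph of Study Procedures requires patients to be "expected to survive and remain in the ICU for at least 96 hours after entry"; criterion 4 requires them to be "expected to survive and remain in the ICU for at least 72 hours after entry".

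**The concern.** An eligibility threshold decides who is randomised, so an error here carries through to every estimate. Staff have two courses open to them, and both cause harm.

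If they follow the text, the 28-day infection comparison (Aim 1) and the agreement between the Harris-Benedict estimate and measured resting energy expenditure (Aim 2) are estimated only above a BMI of 40. The agreement result is especially exposed, because the Background explains that the Harris-Benedict equation is built partly from weight and height. A Phase III trial in ICU patients generally would then be designed from a narrow and unusual group.

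If they enrol on what they presume was meant, every randomised patient with a BMI of 40 or less fails a written criterion. The Aim 1 analysis commits to intention-to-treat with all data from all randomised subjects, so these patients could not simply be dropped afterwards.

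**Working it through.** There is no figure in the plan to reproduce: the protocol gives no BMI distribution and no power calculation for the primary endpoint. The check is mainly a comparison of the text, section by section.

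**1. Literal effect of the criterion.** Patients must meet the listed criteria, and criterion 3 requires a BMI above 40. All 3 × 20 = 60 subjects must therefore be above 40, and a patient at 40 or below cannot enter.

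**2. What the other sections say about body size.**

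| Section | Population or relevant content | Obesity or BMI restriction? |
|---|---|---|
| Title | Critical illness | None |
| Abstract | ICU patients who need PN because of intestinal failure or dysfunction | None |
| Background | Malnutrition and energy deficit in the ICU | None |
| Hypothesis, Specific Aims | ICU patients; medical and surgical ICU patients on PN with or without EN | None |
| Study Procedures, opening paragraph | Medical or non-neurological surgical ICU | None |
| Inclusion criterion 3 | BMI above 40 | **Yes** |
| Exclusion criteria | Nine items | None |
| Study Schema | Critically ill medical and surgical patients on PN with or without EN | None |

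Outside criterion 3, BMI and obesity appear only in the titles of two cited references (numbers 15 and 32).

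**3. Whether the design looks like an obesity trial.** Randomisation is stratified by clinical center and APACHE II score. The prognostic factors in the Statistical Analysis section are gender, race, APACHE group, center, age, SOFA and glucose; BMI is not among them. The protein goal is given per kilogram without stating which weight applies. The Harris-Benedict estimate uses pre-ICU dry weight, with no adjustment for obesity mentioned. Nothing in the design points to a deliberate restriction.

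**4. Illustrative size.** Let *p* be the share of otherwise eligible patients with a BMI above 40. The documents give no value; 3% to 10% is our assumption.

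- Share of the described population excluded = 1 − *p*: 1 − 0.10 = 90%; 1 − 0.03 = 97%.
- Otherwise eligible patients needed for 60 entries = 60 / *p*: 60 / 0.10 = 600; 60 / 0.03 = 2,000.
- If BMI were ignored at enrolment, expected number of the 60 who fail criterion 3 = 60 × (1 − *p*): 60 × 0.90 = 54; 60 × 0.97 = 58.2.

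**5. Expected ICU stay.** A patient expected to stay at least 72 but less than 96 hours meets criterion 4 and fails the opening paragraph.

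**The case against.** The strongest reply is that this is a clerical slip and not a choice of population. Every other description of the population points the same way, and a reversed inequality sign explains the text. On that view, to say the trial cannot answer its question overstates the matter: randomisation still protects the comparison among those enrolled, and only generalisation suffers.

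Most of this is right as to cause. A reversed sign is the likeliest explanation, and internal validity within the enrolled group is not in doubt. It does not remove the problem, because the written criterion is what sites screen against and what compliance is judged by.

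A second reply is that one character may have been corrupted when the file was converted, and that the content of the figure just ahead of the inclusion list is unknown. This cannot be excluded from the text alone. Other inequalities nearby, such as the APACHE II strata of ≤ 15 and > 15, read sensibly. There is one further conflict of this kind: the section on determining energy deficit skips calorimetry when the inspired oxygen requirement is below 60%, whereas the Background names high inspired oxygen as a source of inaccuracy. Those two passages also need reconciling. The conflict does not show whether authors or conversion were responsible, but it is a reason to check the signs against the source.

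Third, the 3% to 10% share is not from the documents, and the screening figures only restate it. That is correct; they illustrate scale, and the finding does not depend on them.

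Fourth, the two stay thresholds can be read together, with the stricter governing. That reading is possible, but the protocol does not state it. The point is separate from the BMI rule and secondary to it.

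**Conclusion.** The concern holds. As written, criterion 3 confines the trial to BMI above 40 and contradicts the population described in every other part of the protocol. Within that group the comparison would be valid; for medical and surgical ICU patients in general, the trial as written could answer its question only by extrapolation. This must be corrected because the rule determines who is randomised.

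Confidence is high about what the text says. The documents do not establish whether the restriction was intended. The contradiction itself needs no numerical assumption; the 90% to 97% excluded and the 600 to 2,000 patients rest wholly on the assumed 3% to 10% share. The 96-hour versus 72-hour conflict is real but of lesser weight.

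**What to change.** First check the sign in criterion 3 against the source protocol. Then take one of two routes by amendment:

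- **If the general ICU population is intended,** make criterion 3 an upper BMI limit or move BMI above 40 to the exclusion list. The two differ for a patient at exactly 40: reversing the sign gives below 40, whereas the exclusion gives 40 or below. The amendment should state which applies.
- **If an obese-only trial is intended,** give the reason and restrict the title, hypotheses, aims and conclusions to that population.

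In the same amendment, state a single expected-ICU-stay threshold in both places. If anyone has already been enrolled, tabulate BMI at entry so that it is clear which rule was applied in practice.

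The first route is a one-line change that widens the eligible pool and costs little beyond routine amendment review. The second leaves the pool as narrow as now written and requires broader edits, and the sponsor would need to show that 60 such patients can be found at the two hospitals.
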